6.2.4 Dimensional Obsessive-Compulsive Scale (DOCS)

The DOCS is a self-reporting measure developed in 2009 designed to capture dimensional or thematic aspects of OCD symptoms as well as their severity (Abramowitz et al., 2010). Each of the four categorised symptom dimensions 1) germs and contamination 2) responsibility for harm, injury or bad luck 3) unacceptable obsessional thoughts and 4) symmetry, completeness and exactness consists of 5-items addressing time, avoidance, distress, impairment and resistance towards both obsessions and compulsions. Patients are asked to rate each of these 20 items based on experiences in the past month on a Likert scale between 0 and 4, with higher scores reflecting greater severity. Benefits of the DOCS are its reported ability to assist in diagnoses of OCD (total scores greater than 18-20) and discriminate OCD from both healthy controls and patients with other anxiety disorders (Abramowitz et al., 2010). Whereas higher sub-scores on specified dimensions may indicate treatment targets or serve as a predictor of response in treatment intervention studies (Thibodeau, Leonard, Abramowitz, & Riemann, 2015). In addition, and unlike various other OCD measures, the DOCS captures avoidance behaviours common in individuals with OCD. The DOCS has excellent to good internal consistency ($\alpha = 0.89 - 0.90$) and demonstrates good convergent validity with the Y-BOCS (r = 0.56).

6.2.5 Structured interview guide for the HAM-D, 17 item (SIGHD-17)

The HAM-D is a 17-item, multidimensional scale designed for clinicians to administer and has been used extensively in clinical trial research (including OCD studies) since the 1960s to assess intervention efficacy (Baer & Blais, 2010; Moritz, Meier, Hand, Schick, & Jahn, 2004). Each item explores common features of depression including depressed mood, feelings of guilt, suicidality, somatic and psychological anxiety and sleep (onset, maintenance early morning wakening). Both the impact and frequency of each item is investigated over the previous 7-day period and a score rated on a Likert scale (ranging from 0-4 for most items) with larger magnitudes correlating with greater severity. Internal consistency appears to be greater when using the structured guidelines for the HAM-D (Williams, 1988), thus, the structured HAM-D (17-tem) will be employed in this study. Inter-rater reliability is high for the HAM-D total score (0.80-0.98), despite being poor for some of its individual items in some instances (Bagby, Ryder, Schuller, & Marshall, 2004). Suggested severities of depression as per the total HAM-D score (17-item) include no depression (0-7); mild depression (8-16); moderate depression (17-23); and severe depression (≥24) (Zimmerman, Martinez, Young, Chelminski, & Dalrymple, 2013).

6.2.6 Barratt Impulsivity Scale-11 (BIS-11)

The BIS-11 is a 30-item self-reporting measure designed to assess personality and behavioral constructs of impulsivity (Patton et al., 1995). It is suggested to be the most commonly employed self-reporting measure used specifically to assess impulsiveness in both research and clinical settings, with over 50 years of use since the creation of its first version in 1959 (Stanford et al., 2009). The BIS-11 consists of three factors of impulsivity 1) motor impulsiveness (11 items) 2) attentional (cognitive) impulsiveness (8 items) and 3) non-planning impulsiveness (11 items). The participant is asked to answer each item on a 4-point Likert scale (1 = rarely/never, 2 = occasionally, 3 = often, 4 = almost always/always). The BIS-11 will be employed in this study at baseline only and used to assess if the degree of impulsivity traits predict treatment response to NAC or placebo.

6.2.7 The Beck Anxiety Inventory (BAI)

The BAI is a 21-item self-reporting instrument which is used widely is clinical research both as a screening and outcome tool to determine the presence and severity of anxiety symptoms as defined by the DSM-IV (Beck & Steer, 1993). It was designed specifically to differentiate between anxiety and depressive symptoms, however, the BAI is advised not to be used as a diagnostic tool (Leyfer, Ruberg & Woodruff-Borden, 2006; Bardhoshi, Duncan & Erford, 2016). Each item assesses the presence and impact of physical and psychological symptoms of anxiety such as the occurrence of a 'racing or pounding heart', 'feeling unsteady' and 'fear that the worst may happen'. Participants are asked to answer each of the 21 items from experiences of the past 7day period on a 4-point Likert scale, with 0 indicating 'not at all' and 3 ' severely', for example 'I could barely stand it'. A total score is obtained by adding all scores from each domain, with 0-7 denoting minimal anxiety, 8-15 mild anxiety, 16-25 moderate anxiety and 26-63 severe anxiety. A recent psychometric meta-analysis involving 192 studies from 1993 has highlighted the BAI to hold an excellent internal consistency ($\alpha = .91$, k = 56, n = 25.917, both clinical and non-clinical samples) and test-retest reliability in clinical samples of r = .65 (k = 10, n = 2,101, Mdn = 6 weeks) (Bardhoshi, Duncan & Erford. 2016).

6.2.8 World Health Organization-Quality of Life-BREF (WHOQOL-BREF)

The WHOQOL-BREF (Skevington et al., 2004) is a culturally appropriate quality of life (QOL) assessment instrument, which assesses an individual's perception of personal goals, standards and concerns, in the context of his/her culture and value systems. The WHOQOL-BREF is a reduced version of the original instrument, designed for use in clinical trials. It comprises 26 self-report items, including two benchmark items assessing overall QOL and general health. The remaining 24 items cover the domains of physical health, psychological health, social relationships, and environment. The WHOQOL-BREF also provides an overall score relating to QOL and general health. Individuals are asked to indicate "how good", "how satisfied", "how completely", "how often" or "how much" they experienced or felt relevant concerns over the past four weeks on a five-point Likert scale. The two benchmark items (overall QOL and general health) are calculated as a single score with a range of one to five. Domain scores are calculated by multiplying the mean score for all items included in each domain by a factor of four. Potential scores for each domain range from four to 20, with higher scores indicative of greater QOL.

Research indicates the WHOQOL-BREF is a valid and psychometrically sound instrument. Cross-sectional data obtained from a survey of adults (general population, in addition to hospital, rehabilitation, and primary care settings) carried out in 23 countries (N = 11,830) has indicated the WHOQOL-BREF has good psychometric properties of reliability (Cronbach's alphas ranging from .76 for social relationships to .87 for environment) and performs well in tests of validity (Fu et al., 2013; Skevington, Lotfy, & O'Connell, 2004).

6.2.9 Sheehan Disability Scale (SDS)

The Sheehan Disability Scale (SDS), developed in 1983, measures the extent in which three major domains (work, social life or leisure activities, and home life or family responsibilities) in an individual's life are impaired by their mental health symptoms. In this study, the scale will be employed as a self-reporting measure where participants will be asked to rate impairment on a 10-point visual analog scale which is anticipated to be completed within 1-2 minutes. A study involving 1,001 primary care patients highlighted that the inter-item correlations of the three SDS domains were fairly high (0.70 for work and family impairment, 0.72 for work and social impairment, and 0.79 for family and social impairment) (Leon, Olfson, Portera, Farber, & Sheehan, 1997). Consequently, the internal consistency was also high (alpha = 0.89 for the three item scale). Further, with effective treatment, the SDS appears to reflect chance over time and does not discriminate between active treatment (even in studies involving two active treatment arms) or placebo (Arbuckle et al., 2009; Leon et al., 1997).

6.2.10 Clinical Global Impression Scale (CGI)

The CGI was first developed for use in 1976 as part of a National Institute of Mental Health psychopharmacology study for schizophrenia (Guy, 1976). It is now widely used as a standard primary measure across various psychiatric conditions including depression, bipolar and OCD to assess treatment interventions (Berk, Copolov et al., 2008_a; Dean et al., 2014; Haghighi et al., 2013). The CGI is clinician rated and consists of two domains; the first rates the severity (CGI-S) of the participant's condition at baseline and each following visit, whilst the second domain rates the participant's perceived improvement (CGI-I) from baseline. The CGI-S scores range from 1-7, one being 'normal' and seven 'extremely ill'. The researcher rates the participant's primary condition in question each visit, based on their own observations and judgement, as well as self-reports obtained from the participant. The CGI-I assesses the clinical change compared to the

CGI-S score at baseline on a similar 1-7 scale, with one being 'very much improved' and seven 'very much worse'. Conjointly, higher scores on the CGI equate to greater severity and worsening symptoms. The CGI is a valid outcome measure in psychiatry and has been supported in a study comparing over 600 hospital admissions and over 600 discharge rates, which were positively correlated with both CGI-I/S scores (r = .40 and .71 respectively; Berk, Ng et al., 2008). In addition, these results highlight this scale's sensitivity to change.

6.2.11 Patient Global Impression of Change (PGI)

The PGI is a self-reported scale consisting of two parts which asks patients to rate the severity of the disease or disorder in question (the PGI-S) on a four point scale, for example, 1 = 'normal', 2 = 'mild', 3 = 'moderate' or 4 = 'severe'; as well as its perceived improvement across the course of the intervention (the PGI-I) on a seven point scale (1 = very much better, 7 = very much worse). Congruent with the CGI, PGI-S and PGI-I scores of higher magnitude correlate with greater perceived severity and worsening of symptoms.

6.2.12 Dietary Questionnaire for Epidemiological Studies (DQES v3.2)

The DQES v3.2 is a modification of the Food Frequency Questionnaire (FFQ) developed by the Cancer Council in the late 1980s. It assesses the average intake of five food groups (1. Cereals, sweets & snacks 2. Dairy product, meats and fish 3. Fruit 4. Vegetables and 5. Alcoholic beverages) consumed over the last 12 months, and includes over 80 food items as well as approximate portion sizes. Each participant's questionnaire will be analysed by the Nutritional Assessment Office of the Cancer Council Victoria to determine intake of energy, fat, (saturated fats and poly & mono unsaturated fats), fatty acids, cholesterol, protein, carbohydrates, sugars, starches, fibre, alcohol, various antioxidants, vitamins and minerals and glycaemic index and load of their diet. A URL will be provided for participants to complete the DQES v3.2 at home, alternatively, if they do not have internet access at home, they can complete the questionnaire on site on a study laptop.

6.3 Physical Examination

6.3.1 Blood pressure

Given NAC's potential hypotensive activity, participants will have their blood pressure (BP) taken automatically via a BP machine in each study visit. BP will be measured when participants are in a seated position, legs uncrossed, the BP cuff on their left arm and arm resting at heart level. BP will be categorized according to international guidelines, as seen in Table 6.1 below.

Table 6.1 International Blood Pressure Categorisations

Blood Pressure Classification	SBP mmHg		DBP mmHg
Hypotension	<90	or	<60
Normal	<120	and	<80
Prehypertension	120–139	or	80–89
Stage 1 Hypertension	140–159	or	or 90–99
Stage 2 Hypertension	≥160	or	≥100

6.3.2 BMI

Participants' height (m) and weight (kg) will be taken at baseline using a retractable tape measure and an electronic set of scales. These values will be used to calculate participants' body mass index (BMI; weight in kilograms/height in metres²).

6.4 Clinical Laboratory Investigations

Participants may consent to providing a blood sample which will be analysed for single nucleotide polymorphisms (SNPs). Consenting participants can have their blood taken on site by an RA trained in venipuncture, or they will be given a pathology slip for ACL and asked to complete the blood test offsite at a time and ACL location of their convenience. A total of 5ml of blood will be extracted and collected in an EDTA tube by a venipuncture technician which will be couriered to ACL Molecular Genetics Lab and stored as whole blood at -80°C. DNA will be extracted from this sample and analysed for various SNPs, names of which are yet to be confirmed by the study

investigators. No SNPs will be analysed until appropriate ethics committees have approved an amended SNP list in this protocol.

The samples will be stored for a period of up to five years after completion of the study and analysed to provide data for the current study, and possibly other research studies relating to OCD with appropriate ethics approval (where consent has been provided by participant).

7 ASSESSMENT OF SAFETY

7.1 Methods and Timing for Assessing, Recording, and Analyzing Safety Parameters

7.1.1 Adverse Events

ICH E6 defines an adverse event (AE) as any untoward medical occurrence in a patient or clinical investigation subject administered a pharmaceutical product regardless of its causal relationship to the study treatment. An AE can therefore be any unfavorable and unintended sign (including an abnormal laboratory finding), symptom, or disease temporally associated with the use of the IP. The occurrence of an AE may come to the attention of study personnel during or by communication in between study visits or the participant presenting for medical care.

[name], [name] and [name] will be available for medical supervision relating to the participants in the study at The Melbourne Clinic. [name] and [name] will provide medical supervision at The Royal Brisbane and Women's Hospital and [name] at Western Sydney University.

7.1.2 Serious Adverse Events

A serious adverse event (SAE) includes any untoward medical occurrence that:

- results in death;
- is life-threatening (including suicide attempts. NOTE: The term "life-threatening" refers to an event/reaction in which the patient was at risk of death at the time of the event / reaction; it does not refer to an event/reaction which hypothetically might have caused death if it were more severe);
- requires inpatient hospitalisation or prolongation of existing hospitalisation;
- congenial anomaly/birth defect
- results in persistent or significant disability/incapacity;
- is a medically important event or reaction

7.1.3 Screening for suicidality

Suicidality is screened by item-3 of the SIGHD-17 at each study visit (with the exception of the initial baseline 2 session, where the SCID-CT-5 will be used). Participants are also asked at the beginning of each follow-up visit regarding worsening of mood, OCD symptoms, thoughts of self-harm and suicidal ideation. Participants will be withdrawn from the study if item-3 on the SIGHD-17 is equal to or greater than 3 and if not at immediate risk, will be advised to make contact with their treating doctor. In cases of strong suicidal ideation and intent (for example, SIGHD-17 item-3 score of 4), the participant will be asked to wait with the RA until a risk assessment can be conducted by one of the medical investigators on site. If necessary, the participant will be directed to emergency services or 000 will be called for immediate transfer. The participants treating psychiatrist or physician will be contacted immediately.

7.1.4 Procedures to be followed in the Event of Abnormal Laboratory Test Values or Abnormal Clinical Findings

In the event of high or low blood pressure (see table 6.1), participants will be asked to have their BP taken again by the RA before completion of the study visit. Recent intake of caffeine, alcohol, medication and cigarettes, exposure to cold temperatures as well as recent stressors, or feelings or stress will be ascertained. If the 2nd reading appears abnormal, they will be advised to see their GP or treating doctor.

7.2 Reporting Procedures

Any AE or SAE may be reported by a participant in person during one of the study visits, or via phone as the event occurs. Participants will be advised at the baseline screening session (and in sessions thereafter) to contact the RA as soon as possible in the event of an AE or SAE. A landline number will be provided to participants to enable contact during business hours, however, if the event occurs after hours, they will be advised to call a specified research study mobile number which the principal investigator or CTC will keep with them at all times.

7.2.1 Serious Adverse Events

If any SAE (outlined in 7.1.2) occurs within the study they will be reported to all ethics committees (TMCREC, The University of Queensland Medical Research Ethics Committee and WSU Human Research Ethics Committee) within 48 hours of occurring using the initial SAE report form (see appendix). Subsequently, a follow-up SAE form (see appendix) will be submitted two weeks later to inform the ethics committee of the outcome of the event. The RA will keep appropriate contact with the participant throughout the period of the SAE and monitor after its resolution where applicable, and record all methods of contacts and details in their CRF.

7.2.2 Adverse Events

At the beginning of every follow-up visit, participants will be questioned non-specifically for any adverse events (AEs) as well as asked to complete a purpose-designed Symptom Checklist (the Systematic Assessment for Treatment Emergent Events; SAFTEE) to determine if a participant experienced an AE. Any verbally reported AEs or any symptoms on the SAFTEE marked as causing significant distress, including local and systemic reactions not meeting the criteria for a SAE, will be recorded in the participant's CRF. The information recorded in the CRF will be based on signs and symptoms reported by the participant or observed by the investigators. All AEs will be discussed with the study investigators in weekly teleconferences relating to the progress of the study and any necessary intervention for AEs will be decided by the medical investigators.

A description of each event, date and time of onset, assessment of severity, suspected relationship to study product (assessed only by those with the training and authority to make a diagnosis, which would include an MD or psychiatrist), and time of resolution/stabilization of the event. All AEs occurring during the study must be documented appropriately regardless of relationship. All AEs will be followed to adequate resolution, and if a participant experiences an AE or an SAE during the treatment period that has persisted through to the last testing day, consent will be requested for continued contact with the participant until the AE or SAE has fully resolved. The status of the participant's condition will be recorded in their CRF each time contact is made.

Any medical condition that is present at the time that the patient is screened should be recorded in their medical history and not reported as an AE. However, if this condition deteriorates at any time during the study, it should be recorded as an AE.

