5.4 Assessment of Subject Compliance with Study Intervention/Investigational Product

Participants will be asked to return their IP container from the previous 4-weeks with any remaining capsules left inside at each follow-up visit. The RA will give the container to a third party who will count any remaining capsules and record the value into the participants CRF. The days since last visit will be determined and the expected amount of capsules to be taken by the participant during this time calculated, for example, 28 days x 6 capsules per day (3,000mg of IP) = 168 capsules. This value will be subtracted from the amount of capsules that were in the container upon dispensing, and compared with the amount of capsules returned by the participant to determine compliance.

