5.10 Follow-up visits

Participants will be required to attend follow-up visits at Week-4, 8, 12, 16, 20 and 24. In these sessions, participants will be asked to provide an overview since their last visit, particularly any noticeable changes in their OCD, mental health, functioning and/or quality of life. Changes in treatment (pharmacological and/or psychological), drug and alcohol consumption, medical conditions and the occurrence of side effects, if any, will also be ascertained. The Y-BOCS symptom checklist will be re-administrated by the RA to identify current obsessive and compulsive symptoms, followed by Y-BOCS severity scale (including question 11 regarding insight) and SIGHD-17. At each follow-up visit, the participant will also be asked to complete the DOCS, BAI, SDS, PGI-S, PGI-I and SAFTEE. Upon conclusion of each follow-up visit, the participants blood pressure will be taken and the CGI-I and CGI-S completed by the RA. In addition, at Week-12 and Week-20, the WHOQOL-BREF will also be completed by the participant.

Participants will also be reimbursed for travel expenses totaling \$140-\$160 in the form of Coles/Myer gift cards (\$20 at each scheduled visit; \$160 in total if all study visits are completed and if the baseline sessions are completed on separate days, reflecting additional travel costs incurred to the participant).

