6.2 Clinical Evaluations

6.2.1 Qualitative review

At the beginning of each follow-up visit, participants will be asked to provide an overview of their month. Specifically, the RA will use the following semi-structured, open-ended questions to assist in gathering qualitative data:

- What, if any, changes have you noticed about your OCD over the past four weeks?
- What do you think has brought on these changes OR why do you think things have remained unchanged?
- Have you noticed differences in any other areas of your life over the past four weeks? (can prompt with...) For example, sleep, mood, energy, social life, work, stress...

Detailed notes will be taken by the RA during and after each visit, capturing as much information and narrative as possible provided verbally by the participant and also including the RAs own observations. The RA's impression of the participant's status and progress will also be detailed.

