6.2.2 Yale Brown Obsessive-Compulsive Scale (Y-BOCS) – severity scale

The Y-BOCS (severity scale) was created in 1989 by Goodman and colleagues and is typically administrated as a 10-item instrument to provide a rating of severity regarding OCD symptoms. It is widely used in OCD clinical research and private practice and is well regarded as the gold standard for measuring the severity of both the obsessions and compulsions present in the disorder (Rapp, Bergman, Piacentini, & McGuire, 2016). Treatment sensitivity of the Y-BOCS has been demonstrated through its extensive use in clinical trials for OCD (Grabill et al., 2008). The Y-BOCS is a semi-structured, clinician administrated scale that asks the patients to reflect on the most prominent obsessive and compulsive symptoms separately over the past seven days, exploring frequency, impact/interference, distress caused and the person's effort to resist and ability to control the thoughts. A five point Likert scale ranging from 0-4 is used for each question, 0 equating to none or minimal impact/intensity and four of greatest severity. Scores are determined by the researcher based on the participant's self-reports as well as the researcher's own observations and interpretation during the session. The sum of the 10 items yields an overall score, which enables participant's OCD to be categorised as sub-clinical (0-7), mild (8-15), moderate (16-23), severe (24-31) and extreme (32-40). The Y-BOCS has demonstrated good criterion-related validity as patients diagnosed with OCD have received higher scores on the Y-BOCS compared to those with other anxiety disorders and healthy controls (Grabill et al., 2008). In addition, question 11 of the Y-BOCS will be administered at each visit which assesses the participant's insight into their obsessive and compulsive symptoms. A rating of excellent (=0), good (=1), mild (=2), poor (=3) and completely lacking insight (=4) can be determined on a Likert scale of 0 - 4, however, these scores are not included in the Y-BOCS total score.

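### At the double-blind visits (W4–W20) side effects are asked about before the Y-BOCS and SIGHD-17 are rated, and blood pressure is taken before the CGI, giving the rater an avoidable cue to allocation

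*Protocol*

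**What the plan says.** Section 7.2.2 fixes the time of the AE enquiry: "At the beginning of every follow-up visit, participants will be questioned non-specifically for any adverse events". It attaches the SAFTEE checklist to the same moment.

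Section 5.10 describes the visit as a sequence. It opens with the participant's overview since the last visit, where "medical conditions and the occurrence of side effects, if any, will also be ascertained". Then: "The Y-BOCS symptom checklist will be re-administrated by the RA to identify current obsessive and compulsive symptoms, followed by Y-BOCS severity scale", and after that the SIGHD-17. The SAFTEE is listed with the self-report forms that follow. At the conclusion of the visit the participant's "blood pressure will be taken and the CGI-I and CGI-S completed by the RA".

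On who does what, section 6.2.1 says of the start of each follow-up visit that "the RA will use the following semi-structured, open-ended questions to assist in gathering qualitative data". Section 5.10 names the RA for the Y-BOCS and the CGI. On how scores are reached, section 6.2.2 bases the Y-BOCS on participant report "as well as the researcher's own observations and interpretation during the session", and section 6.2.10 describes the CGI in similar terms.

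Two other cues are controlled. Section 5.1.2 puts a sachet of NAC powder in all product so that odour does not reveal the arm to participants or RAs. For compliance, section 5.4 provides that "The RA will give the container to a third party who will count any remaining capsules".

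**The concern.** Section 2.3.1 lists effects that NAC may cause: abdominal discomfort, heartburn, diarrhoea, flatulence, nausea and cramps. Section 6.3.1 gives NAC's potential hypotensive activity as the reason for measuring blood pressure. A rater who has just heard or seen such findings may revise a private guess of the arm, and the next task is the primary outcome rating. If these findings differ in frequency between arms, and the guess moves the score, the result is a rating difference between arms that is not a treatment effect. Neither randomisation nor the MMRM in section 8.1 removes it.

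The Y-BOCS also decides non-response for titration in section 5.2, so a shifted score could reach the dose received as well as the outcome.

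**Working it through.** The point turns on order and roles, so the main check is to set the sections side by side.

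| Step | 5.10 | 7.2.2 | Performed by |
|---|---|---|---|
| Spoken side-effect question | with the opening overview | beginning of visit | RA, by inference |
| SAFTEE | listed after the ratings | beginning of visit | participant |
| Y-BOCS checklist and severity scale, SIGHD-17 | after the overview | – | RA |
| Blood pressure | at the conclusion, before the CGI | – | not named |
| CGI-I, CGI-S | at the conclusion | – | RA |

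1. **Order.** Both sections place the spoken question before the Y-BOCS. In 7.2.2 this is explicit; in 5.10 it follows from the order of description. They disagree on the SAFTEE, but the point does not depend on which is right.
2. **Person.** The AE sentence in 7.2.2 is passive. That the RA asks is read from 5.10 and 6.2.1, and no section gives the task to anyone else.
3. **Safeguards.** The controls in 5.1.2 and 5.4 cover odour and capsule counts. Neither covers AEs.
4. **Visits.** The concern covers W4 to W20. In the W20–W24 run-out everyone takes placebo and the researchers know it (4.3.1, 5.12).

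**Size, by assumption only.** The protocol gives neither AE rates by arm nor a rating shift. Assume:

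spurious difference = (excess proportion with recognisable AEs on NAC) × (rating shift in those participants)

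Section 8.1 equates f = 0.15 with 3 points. With d = 2 × 0.15 = 0.30, the implied SD is 3 / 0.30 = 10. Assuming a within-person correlation of 0.5, seven time-points and 100 per arm:

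SE = 10 × √((1 + 6 × 0.5)/7) × √(2/100) = 1.07

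| Assumed excess | Assumed shift | Spurious difference | Share of 3 points | Two-sided type I error (nominal 5%) |
|---|---|---|---|---|
| 0.10 | 1 | 0.1 | 3% | 5.1% |
| 0.20 | 2 | 0.4 | 13% | 6.6% |
| 0.30 | 3 | 0.9 | 30% | 13.4% |

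An assumed excess of 0.40 with a 3-point shift gives 0.40 × 3 = 1.2 points, or 40% of the target. If the shift ran against NAC, power for 3 points would fall to about 77% at 0.1 points and 50% at 0.9.

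Two features make these figures generous. They count the effect of all AE knowledge, not the part due to question order. They also spread the shift over all seven time-points, whereas the concern touches five (W4, W8, W12, W16, W20).

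**The case against.** The strongest reply is that allocation stays concealed. An outside person holds the code (4.3.2), capsules and containers are identical (5.1.2), and no group label appears (4.3.1). A reader might infer from the visit order that raters are unblinded; the protocol does not support that. Hearing of an AE permits a guess and no more. The guess is a weak one, since section 4.1 requires concurrent psychotropic medication and section 5.5 permits many agents. This stands, and it limits the point to a risk.

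A reader might also infer that NAC will show more AEs than placebo and that ratings will move in a known direction. Section 2.3.1 says only what NAC may cause, calls some of it mild, and gives no comparison with placebo. A rater who suspects NAC could score lower or higher. This stands too.

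On the 5.10 reading of the SAFTEE, only a non-specific question precedes the Y-BOCS. That narrows the cue, but 7.2.2 says otherwise, and even a non-specific question invites a report.

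Reordering also leaves other routes open: the opening qualitative review (6.2.1), AE reports made to the RA (7.2), tolerance calls (5.2, 5.9), weekly teleconferences (7.2.2, 10) and recall from earlier visits. This is correct, and it makes the gain partial.

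Finally, visit order may be set in the procedures mentioned in sections 10 and 12.5, which are not at hand. But 7.2.2 itself fixes the AE enquiry at the start, so a worksheet with another order would contradict it.

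**Conclusion.** The point holds as a design weakness at W4 to W20: the protocol places an avoidable cue to allocation just before the primary rating, while guarding the same raters against odour and capsule counts. It rests on reading 5.10 as a sequence and on the inference that the RA asks about AEs.

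No size or direction can be derived. The 0.1 to 1.2 points above are arithmetic on assumed inputs, and the share due to question order is unknown and could be close to zero. It would be wrong to report that the trial's result is biased, or that up to 40% of the target effect is at risk. The change is worth making because it is cheap, not because harm has been shown. The disagreement between 5.10 and 7.2.2 on SAFTEE timing needs reconciling in any case.

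**What to change.** Reconcile 5.10 and 7.2.2 to one visit order for W4 to W20:

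1. Questions on worsening mood and self-harm, kept at the start as section 7.1.3 has them.
2. Y-BOCS checklist and severity scale, SIGHD-17, CGI-S and CGI-I, scored and closed.
3. The AE question, the SAFTEE, blood pressure and, where feasible, the open-ended qualitative review of 6.2.1.
4. Any dose decision and dispensing, after the AE enquiry and within the same visit, so that the information section 5.2 calls for is in hand.

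The cost is edits to 5.10 and 7.2.2, to 6.2.1 if the review moves, and a reordered visit worksheet. No assessment or staff is added. The downside is that the AE enquiry comes later in the visit. The gain is partial, because RAs may still know of AEs from earlier visits, calls and teleconferences.

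Optionally, where a site has more than one RA, an RA who does not rate that participant could make the tolerance calls. That would also require editing 5.2 and 5.9.
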